Treatment of mild cognitive impairment with transcutaneous vagal nerve stimulation

NCT03359902

1/1/2018

C6.1 Data analytic strategy [name] (Co-I, biostatistician) will conduct the statistical analyses, which will be performed using statistical software, R or SAS. First, standard summary statistics will be provided for all measures (including behavioral and demographic [e.g., sex] measures, volumetrics from T1 weighted images, white matter integrity on DTI and white matter hyperintensities from FLAIR, and baseline neuropsychological test performance) by treatment (sham or active during the first stimulus session). Second, hypotheses will be tested with formal inferential techniques. Third, exploratory analysis for baseline neuropsychological test performance, brain regional volume, and other regional indices from DTI for predicting treatment response will be conducted. We will adjust for multiple comparisons by controlling the false discovery rate and determine statistical significance for each aim. The crossover design will increase the precision, where each subject serves as his or her own control and within subject comparison can be used. The increased power with greater precision to estimate the treatment differences reduces the necessary sample size. Despite this advantage, a potential problem in a crossover design is that carryover effects may bias the direct treatment effects. To account for the potential carryover effects, we will consider the following mixed-effect model. Let y_{ijk} denote the memory score measured at time period k from the j th subject in sequence i ,

$$y_{ijk} = \mu + \beta_{j(i)} + \gamma_k + \tau_{d(i,k)} + \lambda_{c(i,k)} + \epsilon_{ijk},$$

where i =sequence (tVNS-sham or sham-tVNS), j =subject, k =period, μ is the overall mean, δ_i is the fixed effect of sequence i , $\beta_{j(i)}$ is the random effect for patient j with sequence i , γ_k is the effect of period k , $\tau_{d(i,k)}$ is the direct effect of the treatment applied during period k in sequence i , $\lambda_{c(i,k)}$ is the carryover effect of the treatment applied during period k in sequence i , and ϵ_{ijk} is the random error effect. Note that there is randomization of the subjects to the sequences. If the outcome measures do not follow a normal distribution, certain transformation, e.g., a Box-Cox transformation, will be applied before modeling. With this mixed-effect model, various hypotheses on the treatment effects, period effects and carryover effects can be separated and tested. If the carryover effect is not significant between the two sequences, then the data from two periods can be combined and analyzed. In the case that the carryover effect is significant, the overall conclusion about the treatment effect would be in question, however, the data from the first time period can still be used in testing for treatment effects because there would be no carryover from any previous applications of the treatments. Further, we will conduct secondary analysis for investigating the effect of tVNS on the other cognitive domains including language (phonemic and semantic fluency) and executive functions. To identify the factors that mediate the effects of tVNS, i.e., testing the hypothesis in Aim 2, the memory scores will be regressed on the selected factors, such as baseline memory performance (flat learning curve, poor free recall, reduced recognition memory; reduced working memory and poor retrieval with intact recognition), and hippocampal/entorhinal cortex volume (normalized by intracranial volume). Important covariates such as sex, age and education will be adjusted in the regression model if they relate significantly to the outcome variables. Variable selection can be conducted for the model under the standard Bayesian or frequentist framework. For example, a L1-penalty⁴⁹ might be used in variable selection under the frequentist framework. In addition to the plain linear regression model, the generalized additive model⁵⁰ will also be tried for the problem, which is expected to fit the data better and have a better power to detect the factors that are truly associated with the effects of tVNS.

C6.2 Power and sample size considerations The enrollment sample of 60 participants is intended to provide data on the impact of tVNS on the cognitive performance in participants with MCI and predictors of improvement with treatment including brain volume changes associated with AD pathology. Further, these data will be used to indicate feasibility of a larger trial and to provide descriptive estimates of acute effects. To get a rough idea for the effectiveness of the trial, we made the following calculation. Assuming $\alpha = 0.05$, two-sided test, and 60 participants in total. If the carryover effect is negligible, we will have 90% power to detect an effect size of 0.604 for memory improvement in hypothesis 1 in aim 1 based on within subject comparisons. In the case that the carryover effect is significant and we use the first period data only (similar as in a parallel design), we will have 90% power to detect an effect size of $d=0.854$ for aim 1. For the regression analysis in predicting treatment response in aim 2), we will have 90% power to detect a factor that has a marginal correlation of $r=0.43$ with the response variable.

Overall, our methodology and analyses offer a comprehensive approach to understanding the mechanism of action of tVNS as a potential enhancer of cognition affected by decline in the continuum of AD. Our strategy should establish feasibility and our personalized medicine approach will allow us to interrogate treatment responsiveness and examine predictors of said responsiveness. Subsequent larger scale clinical trials including biomarkers such as amyloid imaging, CSF tau, and genetic subtypes (APOE) and longitudinal evaluation of sustainability of effects and whether decline in functional status can be achieved will follow.

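### Aim 1 model: with the sequence effect it is not estimable, without it the treatment estimate is between-subject, and the model behind the 0.604 figure is never written

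*SAP*

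**What the plan says.** SAP C6.1 introduces its only written model for Aim 1 with "To account for the potential carryover effects, we will consider the following mixed-effect model". The displayed equation has an overall mean, a random subject effect, and period, treatment and carryover effects, plus error. The definitions below it add a term that "is the fixed effect of sequence i". They describe the carryover term as one that "is the carryover effect of the treatment applied during period k in sequence i". The indices are "sequence (tVNS-sham or sham-tVNS), j =subject, k =period", so the design has two sequences and two periods.

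The SAP then says that with this model "various hypotheses on the treatment effects, period effects and carryover effects can be separated and tested". Two branches follow: "If the carryover effect is not significant between the two sequences, then the data from two periods can be combined and analyzed"; otherwise the treatment conclusion is in doubt, but "the data from the first time period can still be used in testing for treatment effects".

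C6.2 powers each branch with 60 participants and two-sided alpha 0.05. It gives 90% power at an effect of 0.604 within subjects if carryover is negligible, and at d = 0.854 from the first period only. No level is given for the carryover test, and no within-subject correlation.

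**The concern.** C6.1 justifies the crossover by the precision gained when each participant is their own control. A model that carries a carryover term in a two-period, two-sequence design cannot keep that gain. An analyst who fits the displayed equation gets a between-subject treatment estimate. An analyst who adds the defined sequence effect gets a model that is not of full rank, where the reported result can depend on which redundant term the software drops. The model that yields the within-subject estimate has to be inferred from a remark that the two periods can be combined.

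The branch rule adds a second problem. The carryover test and the first-period treatment test use largely the same data, so choosing the analysis by the first distorts the error rate of the second.

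**Working it through.** **Inputs.** 60 participants, two-sided alpha 0.05, effects 0.604 and 0.854 (SAP C6.2). Two sequences and two periods (SAP C6.1). Equal numbers receiving tVNS and sham first (Protocol section 7), hence 30 per sequence. Assumed, because the documents give neither: within-subject correlation ρ and the level of the carryover test.

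**Stated power figures.**
- First period only: noncentrality 0.854 × √(30/2) = 3.31 on 58 df gives power 0.902.
- Within subject: with the effect in units of the within-subject error SD, the standard error is √(2/60) and the noncentrality is 0.604 × √30 = 3.31 on 58 df, again power 0.902. Also 0.854/√2 = 0.604.
- Both figures reproduce. The SAP does not state the unit of 0.604. If it were the SD of the paired difference, power would be 0.996, so the within-subject error SD is the unit that fits.

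**Cell means.** Write g for the period effect, t for treatment (tVNS minus sham), and c for the difference in carryover from period 1 into period 2 (after tVNS minus after sham). Without a sequence effect:
- tVNS-sham, period 1: μ − g/2 + t/2
- tVNS-sham, period 2: μ + g/2 − t/2 + c/2
- sham-tVNS, period 1: μ − g/2 − t/2
- sham-tVNS, period 2: μ + g/2 + t/2 − c/2

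**Displayed equation.** Four parameters, rank 4, so the fit to the cell means is saturated. Solving:
- t = first mean minus third mean, with weights (1, 0, −1, 0). This is the period-1 between-group difference, whatever ρ is.
- c = weights (1, 1, −1, −1), the difference in sequence totals, a between-subject contrast.

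**With the sequence effect.** Code sequence as (½, ½, −½, −½), treatment as (½, −½, −½, ½) and carryover as (0, ½, 0, −½). Then carryover = (sequence − treatment)/2 in every cell. There are five parameters and the rank is 4, so the three effects cannot be separated.

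**Sequence, period and treatment, no carryover.** Four parameters, rank 4. Treatment has weights (½, −½, −½, ½), the within-subject contrast. Substituting the cell means gives t − c/2, so any carryover difference biases the estimate by minus half of itself.

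**Precision, in units of the total SD.** The period-1 variance is 2/30 and the within-subject variance is (1 − ρ)/30, a ratio of 2/(1 − ρ).

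| ρ (assumed) | SE, carryover in model | SE, no carryover term | Variance ratio |
|---|---|---|---|
| 0 | 0.258 | 0.183 | 2 |
| 0.5 | 0.258 | 0.129 | 4 |
| 0.8 | 0.258 | 0.082 | 10 |

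**Branch rule.** The period-1 difference and the difference in totals have correlation √((1 + ρ)/2): 0.81 at ρ = 0.3, 0.87 at 0.5 and 0.95 at 0.8. With no treatment effect and no carryover, final tests at 0.05 and 40,000 simulated trials per setting (simulation error about ±0.3 points), the overall type I error over ρ = 0.3 to 0.8 was:
- carryover test at 0.05: 6.9% to 8.2%
- carryover test at 0.10: 7.5% to 9.3%

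Check at level 0.10 and ρ = 0.5: among trials sent to the first-period branch, 36.9% rejected. Then 0.90 × 0.05 + 0.10 × 0.369 = 0.082, which agrees with the simulated 8.2%.

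**The case against.** The strongest defence is that the SAP does not commit to taking the treatment estimate from the model with carryover. It has a two-branch rule, C6.2 powers each branch on its own terms, and Protocol section 7 describes a hybrid design meant to allow a between-subject comparison at the first time point. The loss of within-subject information under carryover is therefore disclosed. This stands. What the SAP does not say is that its displayed model already gives the first-period estimate, or which model to fit when the periods are combined.

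Three stronger readings should be set aside.
- A reader might infer that power at 0.604 falls from 90% to 63%. That pairs the effect size of one branch with the estimator of the other, which the SAP does not plan. The 63% also holds only at ρ = 0; it would be 37% at 0.5 and 18% at 0.8, all assumed.
- A reader might infer that carryover cannot be tested under any version. In the displayed equation it can, if there is no sequence effect, which randomisation to sequence supports.
- Read literally, the definition ties carryover to the treatment of the same period, which would make it identical to the treatment effect. The separate index and the SAP's later remark that nothing precedes the first period show that the previous period's treatment was meant. This is a slip of wording.

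The missing sequence term may itself be a reading loss. The conclusion does not depend on it, because both versions were checked.

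**Conclusion.** The concern holds in this form: no version of the model gives a within-subject treatment effect separated from carryover, and the model to which 0.604 applies is not in the SAP. The algebra rests only on two sequences and two periods, with carryover taken from the previous period. The power figures are sound for their own branches.

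The type I error of about 7–9% under the branch rule is conditional on the assumed ρ of 0.3 to 0.8, carryover test levels of 0.05 or 0.10, normal data and 30 per sequence. The C6.2 figures are offered as approximate and the aims include feasibility, which softens the consequence. Still, this is the only model written for Aim 1, and two analysts following it could report estimates whose variances differ by a factor of 4 at ρ = 0.5 or 10 at ρ = 0.8.

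**What to change.** In SAP C6.1:
- State the Aim 1 model as mean + sequence + random subject within sequence + period + treatment + error, with no carryover term. Take treatment from the within-subject contrast, and make this the primary analysis whatever a carryover test shows.
- Report the sequence contrast descriptively, as sequence and carryover combined.
- Keep the first-period comparison (d = 0.854) as a sensitivity analysis.
- Replace the separability sentence with a statement that carryover cannot be separated from sequence in this design, and word carryover as the effect of the previous period's treatment.

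In C6.2, say that 0.604 refers to this model, and give its unit.

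The cost is wording only; no new data are needed. The downside should be stated openly: freedom from carryover then rests on the gap of at least 7 days between sessions (Protocol section 7 and C3.1), and any carryover difference biases the treatment estimate by minus half of that difference.

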Hypothesis 2: Research has demonstrated that neurodegeneration of medial temporal structures is the best antecedent MRI marker of imminent conversion to AD, with decreased hippocampal volume (left > right) being the most robust. Since the hippocampus receives direct input from the NTS as well as norepinephrine from the LC, those participants with MRI evidence of degeneration of the hippocampus/entorhinal cortex (its direct path connections (using diffusion tensor imaging [DTI])) *will improve during tVNS and the degree of improvement may be related to the degree of atrophy.*

Hypothesis 3: Those patients with MCI who have baseline memory impairment including reduced working memory and poor retrieval with intact recognition will improve with tVNS.

Hypothesis 4: Since norepinephrine is important for the function of the prefrontal-executive systems, patients with deterioration of prefrontal cortex as evidenced by atrophy and/or white matter integrity loss will show improvements in retrieval and working memory with tVNS as assessed by cognitive testing (digit span, free retrieval memory after a delay) and *the degree of improvement may be related to the degree of structural abnormality.*

7. Research Plan: Experimental design The design of the study is a hybrid, crossover trial structure with randomized and counterbalanced order of tVNS or sham tVNS (to control for ability to detect stimulation/placebo effects) administration (see *table 1 for basic design elements*). This will allow us the benefits of both a parallel and crossover design in that we will have equal numbers of subjects who have received sham or tVNS at time point 1 allowing a between subject analysis, while also allowing a crossover analysis. This design also enables the assessment of potential carryover and practice effects. Participants will attend four contact periods: 1) consent, inclusion screening, MRI eligibility and screening, structured history interview; 2) MRI scan; 3) and 4) stimulus sessions separated by at least 7 days, each consisting of the experimental protocol described below.

Intervention	Predictor	Outcome
tVNS versus sham stimulation (counterbalanced)	Baseline/sham cognitive performance	Cognitive performance - Memory, executive function
	Hippocampal/entorhinal volume	
	White matter variables	

Table 1: Intervention, predictors, and outcomes

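### Letting a carryover significance test choose the Aim 1 analysis raises the false-positive rate above 5% and gives little protection against carryover

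*SAP*

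**What the plan says.** SAP section C6.1 fits a mixed model with period, direct treatment and carryover terms, and states that "various hypotheses on the treatment effects, period effects and carryover effects can be separated and tested". It then gives a rule with two branches.

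- Carryover not significant: "If the carryover effect is not significant between the two sequences, then the data from two periods can be combined and analyzed".
- Carryover significant: "the overall conclusion about the treatment effect would be in question", but "the data from the first time period can still be used in testing for treatment effects because there would be no carryover from any previous" application of treatment.

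Section C6.2 gives a power figure for each branch, with 60 participants and two-sided alpha 0.05: 90% power for an effect size of 0.604 using both periods, and 90% power for d = 0.854 using the first period only.

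No level is given for the carryover test, no power for it, and no adjustment for the selection. Section C6.1 also says that δ_i "is the fixed effect of sequence i", yet δ_i does not appear in the displayed equation.

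The protocol (section 7, Experimental design) separates the sessions by at least 7 days and plans balanced sequences: "we will have equal numbers of subjects who have received sham or tVNS at time point 1". It lists carryover assessment among the purposes of the design: "This design also enables the assessment of potential carryover and practice effects".

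**The concern.** The final test is chosen by looking at data that the final test then reuses. Carryover is judged from the difference between sequences in subject totals (period 1 plus period 2). The fallback treatment test is the difference between sequences in period 1. A chance imbalance in period 1 pushes both in the same direction, so the trials sent to the fallback are those in which it is already likely to reject.

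Two things are at stake. The Aim 1 result may not have the error rate on which the power statement rests. And the carryover test, a between-subject comparison with 30 per sequence, may be too weak to protect the two-period result, which is its only purpose. C6.2 wants the same Aim 1 result to inform a larger trial.

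**Working it through.** **Inputs.** From the documents: 60 participants, equal allocation (so 30 per sequence), two-sided alpha 0.05, effect sizes 0.604 and 0.854. Assumed because not stated: between-session correlation r from 0 to 0.9; carryover test level 5% or 10%; normal scores with equal variance in both periods; 0.604 in within-subject SD units (σ_w). All tests have 58 degrees of freedom.

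**Reproducing the SAP's power.**
- Both periods: the treatment estimate has standard error σ_w/√30, so the noncentrality is 0.604 × √30 = 3.31 and power is 90.2%.
- First period: 0.854 × √(30/2) = 3.31, again 90.2%.

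Both figures reproduce, which supports the reading of the units (0.854/√2 = 0.604).

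**Dependence between the tests.** Let σ² be the variance of a single score.
- Period 1 with the total: covariance σ²(1+r), variances σ² and 2σ²(1+r). The correlation is √((1+r)/2), which is 0.71 at r = 0 and 0.95 at r = 0.8.
- Period difference with the total: covariance σ² − σ² = 0. The two-period test is independent of the carryover test.

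**Type I error with no effect and no carryover.** For carryover test level a:

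error = (1 − a) × 5% + a × P(first-period test rejects | carryover test significant)

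The conditional probability comes from simulation. At r = 0.5 and a = 5%: 0.95 × 5% + 5% × 52.7% = 4.75% + 2.64% = 7.4%.

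| r | First-period test rejects, given significant 5% carryover test | Overall error, 5% carryover test | Overall error, 10% carryover test |
|---|---|---|---|
| 0 | 33% | 6.4% | 7.0% |
| 0.5 | 53% | 7.4% | 8.2% |
| 0.7 | 63% | 7.9% | 8.8% |
| 0.8 | 70% | 8.3% | 9.1% |
| 0.9 | 79% | 8.7% | 9.4% |

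Simulation error is about 0.1 point. The two-period test used alone stays at 5.0%.

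**Protection against carryover.** Suppose carryover of 0.604 and no direct effect.
- The two-period estimate is biased by half the carryover, 0.302. Its noncentrality is 0.302 × √30 = 1.65, so with no carryover test it falsely rejects 37% of the time.
- The carryover test has noncentrality 0.604 × √(7.5(1−r)/(1+r)): 1.65 at r = 0, 0.96 at r = 0.5, 0.55 at r = 0.8.

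| r | Carryover detected (5% / 10% level) | Rule falsely rejects (5% / 10% level) |
|---|---|---|
| 0 | 37% / 50% | 26% / 21% |
| 0.5 | 16% / 25% | 34% / 31% |
| 0.8 | 8% / 15% | 37% / 35% |

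The rule helps materially only when the sessions are nearly uncorrelated, which is where a crossover gains least.

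**Power.** With a direct effect of 0.604 and no carryover, the rule lowers power from 90% to about 88% (5% level) or 86% (10% level).

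**Model terms.** The text ties λ to the treatment given in period k. To separate it from τ it has to be read as the previous period's treatment. On that reading the displayed equation (mean, period, treatment, carryover) has rank 4 on the four sequence-by-period means and is estimable. Adding δ_i gives 5 columns with rank 4, so carryover is then aliased with sequence. Separation therefore assumes no sequence effect, which the SAP does not say.

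**The case against.** The strongest reply is that the SAP is cautious. It says the conclusion is doubtful after significant carryover, and only that first-period data can be used. If that barred any positive Aim 1 claim in that branch, the error would be 0.95 × 5% = 4.75% (or 0.90 × 5% = 4.5%), below nominal. But the sentence goes on to retain the first-period test, and C6.2 powers it at 90%, so the plan treats it as a test of Aim 1.

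Other points stand in part.
- The study is also exploratory: C6.2 speaks of feasibility and descriptive estimates and calls its calculation rough. The excess is 1.4 to 4.4 percentage points, and its exact size depends on inputs that the SAP does not give. This tempers the severity but does not remove the defect.
- Alpha 0.05 appears only in the power section, and C6.1 controls the false discovery rate. The figures above are for a single outcome. False discovery rate control takes p-values as valid, so it cannot repair one distorted by selection.
- A washout of at least 7 days makes a carryover of 0.604 unlikely. That is fair, but the inflation is present at zero carryover, and a credible washout is a reason to drop the carryover test as a selector.
- Making the first-period comparison primary would also hold 5% and would remain valid under carryover. It is a legitimate alternative at a heavy cost: at r = 0.5 its noncentrality for the planned effect is 0.604 × √0.5 × √15 = 1.65, or 37% power.
- δ_i may have been lost from the equation when the PDF was read. If so, the aliasing is in the intended model; the main point is unaffected.

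**Conclusion.** The concern holds. As written, the Aim 1 rule has a false-positive rate of about 6.4% to 8.7% with a 5% carryover test and 7.0% to 9.4% with a 10% test, against the 5% used for power. The direction is the same at every correlation from 0 to 0.9. In exchange, the test misses a carryover as large as the planned effect in most trials at r of 0.5 or more, at either level, and it costs 2 to 4 points of power when there is no carryover. These sizes rest on 30 per sequence, normal scores, equal period variances and the assumed correlations and test levels. The exploratory setting makes this less grave than in a confirmatory trial, but Aim 1 is still planned as a formal hypothesis test.

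**What to change.** In SAP section C6.1, delete the rule by which carryover significance selects the analysis. Pre-specify one Aim 1 analysis on both periods: fixed sequence, period and treatment effects, random subject within sequence, no carryover term, and treatment tested within subject. Cite the existing separation of at least 7 days as the protection against carryover.

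To keep the carryover assessment that the protocol promises, always report the carryover estimate with its confidence interval, and the first-period comparison. Label both as descriptive sensitivity results that never replace the primary analysis. Make the equation and text agree on δ_i, define λ as the effect of the previous period's treatment, and state that carryover is estimable only if there is no sequence effect. In C6.2, keep 0.604 as the power statement for Aim 1 and mark 0.854 as applying to the sensitivity comparison.

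This changes wording only: no change to sample size, visits or data. With no carryover it restores the 5% error rate and the 90% power. The downside is that the primary result rests on the washout, and any true carryover biases the treatment estimate by half its size. The reported interval shows readers how much carryover the data leave open.

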A1.4 Methods of stimulating the vagus VNS is FDA approved, but requires surgical implantation of a device in the chest and electrodes placed around the vagal nerve in the neck. tVNS is a non-invasive and promising means of modifying brain function. tVNS stimulates the auricular branch of the vagus (located medially at entry of the acoustic meatus¹³). Because it does not directly stimulate descending cardiac fibers, it does not appear to affect mean heart rate or blood pressure and does not carry the cardiac risks of implanted VNS.

6. Specific Aims:

tVNS has the potential to improve cognition in patients with MCI and may even alter the course of decline. We will employ a multimodal approach including neuropsychological testing, structural and functional MRI to assess changes with tVNS in cognition in patients with MCI in support of the development of a therapeutic role for tVNS in the treatment of this disabling disorder.

Aim 1) Evaluate the influence of tVNS on memory performance in participants with MCI. tVNS may alter the activity of the areas of the brain that are critical for encoding or recalling memories and which are often impaired in patients with MCI. Therefore, tVNS may improve behaviors supported by these networks.

Hypothesis 1: During tVNS, participants with MCI will improve in verbal and visuo-spatial memory compared to off-tVNS performance (sham-stimulation).

Aim 2) Determine mechanisms of treatment response variability. Differences in the etiology and expression of MCI may result in different cognitive responses to tVNS. For example, patients with memory loss may have degeneration of the entorhinal cortex and hippocampus or injury to the frontal subcortical networks. These differences in neuroanatomical involvement produce different kinds of memory impairments. We will examine the relationships between the response to tVNS as a function of differences in baseline cognitive and structural presentation. *Further, in secondary analyses, we will examine the effects of biological variables such as sex and also common changes in the brain associated with aging including changes in healthy appearing white matter (DTI assessed) and white matter hyperintensities (leukoaraiosis as assessed through FLAIR MRI).*

Hypothesis 1: Those patients with amnestic MCI who have baseline memory impairment including flat learning curve, poor free recall, and reduced recognition memory will improve with tVNS treatment.

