Clinical and Health Psychology) that also evaluate patients that will meet our inclusion criteria. We may use certain UF services including I2B2 and Healthstreet.

Additionally, we will request a copy of the State of Florida Voter Registration registry. We will narrow down this list by voters that meet our age range (60-89) and send them an IRB approved flyer. This flyer would provide a brief overview of the study; as well as, study contact information for interested individuals.

C3.1 Procedural sequence The sequence and flow of the assessments to be conducted are as follows. Recruited participants will be screened over the phone after giving verbal consent. Participants will be mailed or emailed a map with directions to our study spaces if they request it. Participants who pass the initial phone screen will then be formally consented with a written ICF and then screened for inclusion/exclusion factors via interview, screening questionnaires, and review of medical records. Individuals who live farther away and are interested in the study but not wanting to make the drive without knowing they qualify for the study will have the option of having the intake administered by study staff at their (the potential participants) home. Any information and forms completed during this intake will be locked in a small filing cabinet and driven back to the University of Florida by study staff. All remaining study visits will be conducted at the University of Florida as usual.

Included participants will then undergo the MCI classification portion of the study, which characterizes the sample, collects covariates for mixed model analysis, and verifies group inclusion. Participants will be randomized between the two arms of the crossover sessions (initial tVNS vs. Sham). Behavioral portions of the testing will then be carried out twice, with at least one week between sessions (to avoid carryover effects). MRI scan will occur at least 72 hours from behavioral sessions.

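### The Aim 2 regression uses memory scores, not the tVNS-minus-sham response, so its coefficients mix prognosis with response to tVNS

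*SAP*

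**What the plan says.** Protocol section 6 sets the question for Aim 2: "We will examine the relationships between the response to tVNS as a function of differences in baseline cognitive and structural presentation". Hypothesis 2 adds that "the degree of improvement may be related to the degree of atrophy". The SAP uses the same language of response in its exploratory-analysis sentence (C6.1) and its Aim 2 power statement (C6.2).

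The model itself is given once, in C6.1: "the memory scores will be regressed on the selected factors, such as baseline memory performance". Volume of the hippocampus and entorhinal cortex is the other factor listed. C6.1 introduces the outcome symbol of its crossover model to "denote the memory score measured at time period k", which is a level and not a change. That crossover model contains no baseline factor and no interaction.

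Three other statements bear on this:

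- Multiplicity (C6.1): "We will adjust for multiple comparisons by controlling the false discovery rate".
- If carryover is significant (C6.1): "the data from the first time period can still be used in testing for treatment effects".
- Predictors (Protocol section 7, Table 1): "Baseline/sham cognitive performance", with cognitive performance as the outcome.

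**The concern.** A regression of a score on a baseline factor shows who scores well. It does not show who gains from stimulation. Baseline memory, the first factor the SAP names, will almost certainly predict later memory whether or not tVNS works. The written analysis would therefore be expected to return predictors of tVNS response even when response does not vary between patients. C6.2 presents the study as examining predictors of responsiveness ahead of larger trials, so a false list of predictors could shape who is enrolled next.

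The error can also run the other way. If patients with more atrophy score lower but gain more, prognosis and modification have opposite signs and cancel. Hypothesis 2 gives no direction for the gradient, so this is a plausible reading of it.

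**Working it through.** **The plan's own figure.** C6.2 states 90% power at r = 0.43, n = 60, two-sided 0.05. By Fisher's z, power = Φ(atanh(r)·√(n−3) − 1.960) = Φ(0.460 × 7.550 − 1.960) = Φ(1.51) = 93.5%. The r detectable at 90% is tanh(3.242/7.550) = 0.405. The stated 0.43 matches 3.242/7.550 = 0.429 before back-transformation. The discrepancy is conservative and a separate matter. Nor does the figure settle the outcome, because the response variable is undefined. A purely prognostic factor correlated 0.43 with the tVNS score would be declared significant in 93% of trials.

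**What each regression estimates.** Let x be the standardised factor, a its slope on the sham score and θ its effect on response.

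- Sham score: slope a
- tVNS score: slope a + θ
- Mean or pooled score: slope a + θ/2
- tVNS minus sham: slope θ

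**Assumptions (none is in the documents).** Scores have unit SD. Session-to-session correlation is 0.7, volume-to-memory correlation a is 0.3 to 0.4, and baseline memory correlates 0.7 (also 0.5) with each session score. Each setting was simulated 20,000 times with n = 60, using least-squares t-tests at two-sided 0.05.

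**No true modification (θ = 0): percentage of trials declaring a predictor**

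| Factor tested | tVNS score | Mean score | Difference |
|---|---|---|---|
| Baseline memory (0.7), volume in model | 100 | 100 | 5 |
| Baseline memory (0.5), volume in model | 90–95 | 95–98 | 5 |
| Volume, baseline memory (0.7) in model | 17–29 | 22–39 | 5 |
| Volume alone | 65–90 | 73–94 | 5 |

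With baseline memory at 0.5 in the model, volume is declared in 28–59% across the two level outcomes.

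Hand checks:

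- Volume alone, tVNS score, a = 0.3: Φ(0.3095 × 7.550 − 1.960) = Φ(0.38) = 65%.
- Volume alone, mean score: the SD of the mean is √((1 + 0.7)/2) = 0.922, so r = 0.3/0.922 = 0.325 and the rate is 72%.
- Volume with baseline memory (0.7), a = 0.3: the partial correlation is 0.3 × 0.3/√(0.51 × 0.91) = 0.132, giving Φ(0.133 × √56 − 1.960) = 17%.

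On a different scale (slope per residual SD), volume-type slopes of 0.2, 0.3, 0.4 and 0.5 give 32%, 61%, 84% and 96% for the tVNS score, against about 5% for the difference.

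**False discovery rate control.** Benjamini-Hochberg over the two factors leaves the 17–39% unchanged: baseline memory is always rejected, so volume is still tested at 0.05. With four null factors added, volume is declared in 8–22%, against 1% for the difference. The adjustment controls error for the hypothesis tested, and here that is the wrong hypothesis.

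**Opposite signs (a = +0.3, θ = −0.3).**

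- Volume alone: the tVNS-score slope is 0.3 − 0.3 = 0 and rejects in 5%. The mean-score slope is 0.3 − 0.15 = +0.15 and rejects in 25%, practically always with the wrong sign. The difference rejects in 82%.
- Baseline memory (0.7) added: 53% (tVNS score), 10% (mean score), 78% (difference).

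**Two points that affect the repair.**

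- First-period data contain no within-person difference. With 30 per arm, the treatment-by-volume interaction keeps 5% error but has 21% power at θ = −0.3, or about 33–35% with baseline memory added.
- The sham score is part of the difference. With no modification their expected correlation is −√((1 − 0.7)/2) = −0.39, and sham performance is declared a predictor in about 87% of trials.

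**The case against.** The best defence is that the sentence is shorthand. The same paragraph gives its target as factors associated with the effects of tVNS. The rest of both documents speaks of treatment response, and C6.1 notes the value of within-subject comparison. Protocol C3.1 says screening "collects covariates for mixed model analysis, and verifies group inclusion". A statistician might well fit a difference, and C6.1 calls the prediction work exploratory. The intent is indeed clear. But the one written specification names a different outcome, defined nearby as a level. C6.1 also says this regression tests the Aim 2 hypothesis, and C6.2 gives it a power figure.

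The rates do rest on assumed correlations. Enrolling on low memory scores, and screening with a different test from those used in the sessions, could weaken them. At a baseline correlation of 0.3 with volume slopes of 0.1 to 0.2, baseline memory is declared in 54–69% of trials, which is still most. With baseline memory (0.7) in the model, volume falls to 10–12% at a slope of 0.2 and 6–7% at 0.1, so for volume the problem may be small.

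The exact cancellation is a chosen example. Once baseline memory is in the model, the expected volume slope has the right sign: about 0.10 − 0.30 = −0.20 for the tVNS score and 0.10 − 0.15 = −0.05 for the mean. What remains is loss of power.

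The plan mentions the first-period fallback only for treatment effects and Aim 1. The sham-score problem arises only if Table 1's predictor is taken literally. Both are safeguards for the repair, not further errors. Finally, Hypotheses 1 and 3 predict improvement within patients of a given profile, which a slope alone does not test. That is a fair addition.

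**Conclusion.** The concern holds and should be fixed. As written, the Aim 2 model does not estimate what Aim 2 asks. That follows from the algebra for any factor with a non-zero prognostic slope and needs no numerical assumption. The size does depend on assumptions: false declaration of baseline memory in 90–100% of trials at correlations of 0.5 to 0.7 (54–69% at 0.3), and of volume anywhere from near nominal to 94%, depending on its prognostic slope and on whether baseline memory is in the model. Neither adding the other listed factor nor controlling the false discovery rate removes the problem. Confidence is high on the mismatch; the rates are illustrative. The Aim 1 analysis is not touched.

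**What to change.** In SAP C6.1, replace the Aim 2 sentence with text such as:

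> For Aim 2 the response is each participant's tVNS-minus-sham difference in memory score, adjusted for sequence and period, regressed on the prespecified baseline factors. Equivalently, treatment-by-factor terms are added to the crossover mixed model. The tVNS effect at given factor values, or within a stated profile, is estimated from the same model.

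Then add:

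- If carryover leads to first-period data only, Aim 2 is tested by the treatment-by-factor interaction in those data, and its low power (about 21–35% in the setting above) is acknowledged.
- The cognitive predictors come from the separate pre-stimulation testing (Protocol C2.4 and C3.1), not from the sham session. Table 1 is aligned with this.
- C6.2 names the tVNS-minus-sham difference as the response variable behind its correlation.

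The SAP's word for these factors, mediators, should be moderators; that is a wording correction only. The cost is SAP text. Participants, visits and data stay the same.
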